7.7 Study Completion

Once a subject has undergone all required study assessments, they will have completed the study.

All study data collected through study completion will be included in the data analysis and maintained as part of the study documentation.

7.8 Study Discontinuation

The study may be discontinued at any time by BVT or applicable regulatory agency. If the study is discontinued before study activities have been completed, all study data collected up to the point of discontinuation shall remain the property of the BVT and will be subject to all applicable patient and data privacy requirements.

8.0 STATISTICAL CONSIDERATIONS

8.1 Introduction

This is a prospective, single-arm, multi-center study to demonstrate the safety and efficacy of the Surfacer® System. Clinical data will be obtained from up to 30 subjects treated with the Bluegrass Vascular Technologies Surfacer System device at a minimum of three (3) sites.

No site will enroll more than 10 subjects. The study population will include patients who are candidates for vascular access with limited or diminishing upper body venous access or pathology impeding standard access methods. Patients who provide consent will be enrolled and undergo the procedure with follow-up at hospital discharge and 7 days post-procedure. Total study duration is anticipated to be 12 months. The study objectives and analytical methods to be used are described herein.

8.2 Study Endpoints

8.2.1 Primary Endpoints

Primary Efficacy Endpoint:

- Rate of safe insertion and patency of CVCs created across venous occlusions.

Primary Safety Endpoints:

- Acute device safety, defined as the absence of procedural complications (hemopericardium, hemothorax, pneumothorax, blood transfusion, resuscitation, emergency post-procedural intervention, transfer to an intensive care unit, and death) at discharge and 7 days post procedure.
- Overall device and procedure related anticipated adverse events compared to historical safety data from CV placement procedures.

8.2.2 Sample Size Justification

A statistically powered sample size calculation is not applicable given the objective of this study. Therefore, the sample size is intended to provide sufficient data to assess basic safety and potential for effectiveness with an acceptable level of outcome evaluation certainty, while not overexposing the target population to the risks associated with an investigational device. The selection of at least 30 subjects is consistent with the range of 10-40 subjects cited as typical for such studies in recent FDA Clinical Investigator Training materials:

<http://www.fda.gov/downloads/Training/ClinicalInvestigatorTrainingCourse/UCM378265.pdf>,
 (Slide 10 of 43 at the above link, Nov. 2013).

Table 12 provides the projected width of the confidence interval for a continuous and for a binary endpoint.

Table 12. Expected results for confidence intervals for continuous and binary endpoints

Sample Size	Continuous endpoint	Binary endpoint
	Width of 95% CI	Clopper-Pearson 95% CI
n = 30	+/- 0.37 x SD	+/- 18.7%

With 30 subjects, the Maximum Clopper-Pearson Exact 95% Confidence Interval for the binary outcome will range from 31.3% to 68.7%, assuming an observed percentage of 50% (Listing 1). As the observed rate increases, the confidence interval will narrow. For example, with 30 subjects and an observed rate of 90% (27 out of 30 successes), the Clopper-Pearson Exact 95% Confidence Interval would range from 73.5% to 97.9%. Note that due to the exact nature of the Clopper-Pearson Confidence Interval, the range will not be symmetric the more the observed rate deviates from 50%.

Listing 1. PASS 13 Output for a Binary Outcome Evaluation

Confidence Intervals for One Proportion

Numeric Results for Two-Sided Confidence Intervals for One Proportion

Confidence Interval Formula: Exact (Clopper-Pearson)

Sample

Confidence Level	Size (N)	Target Width	Actual (P)	Proportion Limit	Lower Limit	Upper Limit	Width If P=0.5	Width If
0.950	30	0.244	0.900	0.735	0.979	0.374		

References:

Fleiss, J. L., Levin, B., Paik, M.C. 2003. Statistical Methods for Rates and Proportions. Third Edition. John Wiley & Sons. New York.

Newcombe, R. G. 1998. 'Two-Sided Confidence Intervals for the Single Proportion: Comparison of Seven Methods. Statistics in Medicine, 17, pp. 857-872.

8.2.1 Secondary Endpoints

Secondary Efficacy Endpoint:

- Surfacer System clinical utility use from insertion into the femoral vein to sub-clavicular exit assessed by the ability of the Surfacer System to facilitate central venous access placement.

Secondary Safety Endpoint:

- Technique Conversion Rate

8.3 Statistical Analysis

8.3.1 Data Reporting Convention

Descriptive statistics will be utilized to summarize the demographic and baseline data.

For continuous endpoints, descriptive statistics will be presented including the number of subjects with the measurement, mean, standard deviation, median, minimum and maximum.

For categorical endpoints, descriptive statistics will include the number with the event or characteristic, the number evaluated, the percentage presented, and 95% exact binomial confidence interval. A critical two-sided alpha level of 0.05 will be carried out for all statistical evaluations.

8.3.2 Assumption Verification

As a routine function, visual inspection and statistical tests will be used during analysis to determine if the study variables are consistent with the assumptions of statistical tests proposed. For continuous outcome variables, visual examination of data symmetry will be initially performed with test of normality to be done by Shapiro-Wilks test or an equivalent, and equal variance assumptions will be tested with Folded F-test or an equivalent. For categorical variables, exact tests will be performed to limit assumptions regarding testing where possible.

8.3.3 Pooling of Study Sites

Data collected across different study sites will be pooled. The justification for pooling data

across sites is made on a clinical basis.¹ A common protocol has been used across different sites with the intention of pooling the data for analysis. Enrollment will be balanced between sites, with no more than 10 subjects enrolled at a single site overall. Every effort will be made to promote consistency in study execution at each site.

8.3.4 Analysis Populations

Enrolled Population:

Study results will be analyzed and reported for all enrolled patients who sign the informed consent, complete the screening procedures are eligible and enrolled in the study.

Intent-to-treat (ITT) Population:

The ITT safety subject population comprises all enrolled subjects in whom Surfacer System usage was attempted (i.e. the first step in the Instructions for Use of the Surfacer System was performed), regardless of whether or not the procedure was completed with the successful placement of a CVC.

Per Protocol Population:

The per protocol (PP) population will include all enrolled subjects in whom the Surfacer System procedure was completed, with a CVC implanted completely and correctly (i.e. the last step in the Instructions for Use of the Surfacer System was performed).

All primary and additional endpoints will be evaluated in both the intent to treat (ITT) and Per Protocol analysis sets. The intent to treat analysis will be considered primary.

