6.4.4 Secondary Safety Endpoint

- Technique Conversion rate.

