7.3 Subject Enrollment

A subject will be considered “enrolled” in the study when they have completed informed consent, are qualified per all study screening requirements and component of the investigational study device is inserted into the subject.

Once a subject has been exposed to the study device, even if the Investigator is unable to complete the Surfacer treatment, the study subject will be considered part of the intent-to-treat population and will be followed up to 7 days post-procedure, or until any adverse events are resolved.

See Section 8.0 for description of analysis populations and statistical considerations.

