8.3.5 Primary Endpoint Analysis

Descriptive statistics reported for both primary safety and efficacy endpoints will be summarized using number with the event or characteristic, the number evaluated, frequencies, percentages and two-sided exact 95% confidence intervals, or time to event analysis, as appropriate. Fisher's exact test will be carried out for independent proportions comparison. A

¹ Meinert, C. (1986). Clinical Trials: Design, Conduct, and Analysis. Oxford University Press, New York.

critical two-sided alpha level of 0.05 will be used for all statistical evaluations. The primary endpoint study outcomes will be evaluated in the ITT population.

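### The Per Protocol set is selected on procedural success, so placement success in it is 100% by construction and aborted cases drop out of its safety result

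*Combined protocol and SAP*

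**What the plan says.** Section 8.3.4 (Analysis Populations) admits to the PP set enrolled subjects "in whom the Surfacer System procedure was completed, with a CVC implanted completely and correctly", and equates this with reaching the final step of the Instructions for Use (IFU). It sets no condition on eligibility violations, major deviations or attendance at the 7-day visit. The same section states: "All primary and additional endpoints will be evaluated in both the intent to treat (ITT) and Per Protocol analysis sets".

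ITT is the primary set. Section 8.3.4 says so and includes every attempted use whether or not a catheter was placed. Section 8.3.5 confirms it: "The primary endpoint study outcomes will be evaluated in the ITT population". Section 7.3 keeps exposed subjects in ITT and in follow-up "even if the Investigator is unable to complete the Surfacer treatment".

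The endpoints affected are:

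- **Primary efficacy** (Section 8.2.1): "Rate of safe insertion and patency of CVCs created across venous occlusions".
- **Primary safety** (Section 8.2.1): freedom from a list of procedural complications at discharge and at 7 days.
- **Secondary efficacy** (Secondary Endpoints, also numbered 8.2.1): use of the system from femoral entry to exit, "assessed by the ability of the Surfacer System to facilitate central venous access placement".
- **Secondary safety** (Section 6.4.4): "Technique Conversion rate", for which no definition is given.

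**The concern.** A per-protocol set normally asks how the treatment performed in subjects managed as the protocol requires. This set asks whether the treatment worked. A subject treated exactly as planned in whom placement failed is removed, while a subject with a serious deviation and a placed catheter stays in.

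Because the entry condition coincides with an endpoint, PP placement success cannot vary with device performance. It would still be reported with an exact confidence interval beside the ITT figure, under a label that invites the reading that this is how the device performs when the protocol is followed. The PP safety result drops subjects according to how their procedure ended, and that may be related to whether they had a complication. The plan is also left with no adherence-based sensitivity analysis.

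**Working it through.** **Inputs from the plan.** Planned n = 30 (Section 6.0). Exact (Clopper-Pearson) two-sided 95% intervals (Sections 8.2.2 and 8.3.5). Illustrative result: "with 30 subjects and an observed rate of 90% (27 out of 30 successes" (Section 8.2.2).

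**Inputs assumed for illustration.** The three failures in that example are non-placements (aborted procedures); two of the 27 placed catheters lose patency; two subjects have a listed complication. The documents give none of these counts.

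**Interval formula.** For x events in n, the lower limit is the 0.025 quantile of Beta(x, n − x + 1) and the upper limit is the 0.975 quantile of Beta(x + 1, n − x). The lower limit is 0 when x = 0 and the upper limit is 1 when x = n.

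**Step 1: reproduce the plan's figures.** 27/30 gives 73.5% to 97.9%, and 15/30 gives 31.3% to 68.7%. Both match Section 8.2.2.

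**Step 2: placement success.** Let s be the number placed among n ITT subjects. ITT = s/n. PP = s/s = 1 for any s > 0.

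| Placed, s | ITT (95% CI) | PP (95% CI) |
|---|---|---|
| 27 | 27/30 = 90.0% (73.5–97.9) | 27/27 = 100% (87.2–100) |
| 24 | 24/30 = 80.0% (61.4–92.3) | 24/24 = 100% (85.8–100) |
| 15 | 15/30 = 50.0% (31.3–68.7) | 15/15 = 100% (78.2–100) |

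The PP estimate stays at 100% even when half the placements fail.

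**Step 3: full primary efficacy endpoint.** Let x be the number of full successes, with non-placements counted as failures. ITT = x/n and PP = x/s, so PP/ITT = n/s. With x = 27 − 2 = 25:

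- ITT: 25/30 = 83.3% (65.3–94.4)
- PP: 25/27 = 92.6% (75.7–99.1)
- Ratio: 30/27 = 1.11

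This endpoint can fall below 100% in PP, because it also requires safe insertion and patency. It is nonetheless above ITT whenever a placement fails and at least one subject succeeds.

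**Step 4: acute safety, as the proportion with a complication.** With two complications in 30, ITT is 2/30 = 6.7% (0.8–22.1). With three aborted procedures, the PP result depends on where the complications fell:

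| Complications in aborted cases | PP (95% CI) |
|---|---|
| 2 | 0/27 = 0% (0–12.8) |
| 1 | 1/27 = 3.7% (0.1–19.0) |
| 0 | 2/27 = 7.4% (0.9–24.3) |

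PP can therefore look better or slightly worse than ITT.

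**Step 5: technique conversion.** If the term means abandoning the Surfacer System, a converted case does not complete the procedure, and the PP rate is 0% by construction. This is conditional, because the term is undefined.

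**The case against.** The strongest reply is that nothing in the plan rests on PP. ITT is primary and retains every attempted use, the study has no powered sample size, and Section 8 sets no success threshold. Sections 8.3.5 and 8.3.6 require the number evaluated beside each categorical result, so 27/27 would stand next to 27/30 and the exclusion would be visible. Section 8.3.8 summarises adverse events without restricting them to PP, so complications in aborted cases are collected and reported. All three earlier series in Table 4 report 100% technical success, and at that rate PP and ITT coincide. Finally, carrying the procedure through to the last IFU step is arguably a form of adherence, the IFU is not among the documents, and how the secondary efficacy endpoint is scored is not spelled out.

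Much of this stands as a limit on the consequences. The primary result is sound, no safety data are lost from the study, and a numerical gap appears only if some placements fail. The 100% result assumes that the secondary endpoint is scored as placed or not placed, which is its natural reading.

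It does not rescue the set. Showing the denominator reveals the selection without making the estimate informative. The IFU gloss does not help either, because Section 8.3.4 itself equates the last step with a catheter fully and correctly implanted.

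**Conclusion.** The concern holds. As written, the PP analysis of placement success carries no information about the device: it returns 100% at any placement rate above zero. In the plan's 27/30 example, with the failures taken as non-placements, PP is 10 percentage points above ITT and the lower confidence limit rises from 73.5% to 87.2%. The PP rate for the full primary efficacy endpoint is inflated by n/s, here 1.11, if non-placements count as failures. PP safety omits aborted cases in every scenario; whether that flatters the device is unknown, and the illustrated range is 0% to 7.4% against 6.7% in ITT. The failure, patency and complication counts are assumptions.

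The primary ITT analysis is unaffected. This is a defect that should be corrected in a supportive analysis prespecified for every endpoint.

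**What to change.** Choose one of two changes to Section 8.3.4.

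1. **Redefine PP by adherence.** PP becomes ITT subjects without a major protocol deviation, whether or not a catheter was placed. The list of major deviations must be fixed before database lock, and preferably before enrolment, because in an open-label single-arm study results are visible long before lock.
2. **Rename and restrict the present set.** Call it the completed-placement set, use it only for post-placement outcomes such as patency, and report insertion success, technique conversion and acute safety in ITT only.

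Under either option, define technique conversion.

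The cost is SAP wording, with no change to enrolment, procedures or the primary analysis. Option 1 needs no new data collection, since Section 10.8 already requires every deviation to be documented and reported, but that section does not grade deviations, so a list of major ones and its application would be added work. Option 2 is the simpler edit, at the price of having no PP analysis of placement or acute safety. Under both, the PP placement figure is no longer an automatic 100%.

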8.3.5 Primary Endpoint Analysis

Descriptive statistics reported for both primary safety and efficacy endpoints will be summarized using number with the event or characteristic, the number evaluated, frequencies, percentages and two-sided exact 95% confidence intervals, or time to event analysis, as appropriate. Fisher's exact test will be carried out for independent proportions comparison. A

¹ Meinert, C. (1986). Clinical Trials: Design, Conduct, and Analysis. Oxford University Press, New York.

critical two-sided alpha level of 0.05 will be used for all statistical evaluations. The primary endpoint study outcomes will be evaluated in the ITT population.

8.3.6 Secondary Endpoints Analysis

For continuous secondary endpoints, descriptive statistics will be presented including the number of subjects with the measurement, mean, standard deviation, median, minimum and maximum. For categorical endpoints, descriptive statistics will include the number with the event or characteristic, the number evaluated, the percentage presented, and 95% exact binomial confidence interval.

8.3.7 Multiplicity

No multiplicity adjustment will be required.

8.3.8 Safety Evaluations and Analyses

Adverse Events will be categorized by serious and non-serious, device or procedure-related and non-device or non-procedure related, and anticipated and unanticipated.

The frequency of each event will be summarized by seriousness, severity and by relationship to the device. Since some subjects may report the same event several times, the occurrence of the highest severity case of the event will be used for the purpose of analysis.

The rates of adverse events will be presented with associated 95% confidence intervals. No statistical hypothesis test will be made. At periodic intervals during study conduct, clinical evaluation of adverse events will be performed by the IDMC.

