9.1 Adverse Event Classification

9.1.1 Adverse Event

An AE is any undesirable clinical event experienced by a subject participating in a study.

The intensity of an AE will be classified as one of the following:

Mild: transient, does not interfere with the subject's daily activities and does not require therapeutic measures

Moderate: Interferes with the subject's daily activities and requires simple therapeutic measure

Severe: Intolerable experiences that interrupt the subject's daily activities and requires substantial therapeutic measures including surgical intervention or hospitalization

The relationship of the AE to the investigational device will be categorized as one of the following:

Not related: No clinical evidence supporting a causal relationship

Related: Clinical evidence supports a definite and certain causal relationship

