9.1.3 Serious Adverse Event/Unanticipated Adverse Device Effect

A Serious Adverse Event (SAE) is an AE that meets one of the following criteria:

- fatal
- life threatening
- results in an unanticipated or prolonged hospitalization
- results in a significant and persistent disability/incapacity
- results in a congenital anomaly or birth defect

An unanticipated adverse device effect (UADE) is any SAE as defined above that is caused by or associated with the device, if that effect, problem, or death was not previously identified in nature, severity, degree of incidence in this protocol.

Additionally, a UADE includes any other unanticipated serious problem associated with the device that relates to the rights, safety, or welfare of subjects.

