Vasospasm - A transient constriction of the lumen of one or more vessels due to contraction of vascular smooth muscle. **Vessel Perforation** - Complete penetration of the vessel wall, with or without self-limited extravasation of blood into surrounding tissues. **Vessel Dissection**- This term applies to unintended injury of femoral or pelvic vessels or the inferior vena cava. Dissection is defined as disruption of the intimal layer that can be detected by contrast angiography, ultrasound, or other imaging modalities. **Aneurysm**- an abnormal blood-filled bulge of a blood vessel and especially an artery resulting from weakening (as from disease) of the vessel.
- **Unintended Embolization or Thrombosis - Embolism** is defined as the unintended entry of air, thrombus, or foreign bodies into the circulation. **Thrombosis** - local coagulation or clotting of the blood in a part of the circulatory system.
- **Arrhythmias**- Development of a new atrial and/or ventricular arrhythmia, exacerbation of a prior arrhythmia or a significant increase in the severity of the current arrhythmia. Event that requires cardioversion or introduction of a pacemaker will be considered a Serious Adverse Event.
- **Neurologic Sequelae including stroke; transient ischemic attack; nerve injury:** **Stroke** - Acute cerebral infarction or hemorrhage confirmed by brain imaging (CT or MRI), or with new neurological abnormalities persisting more than 72 hours. A stroke that occurs within 24 hours of the procedure will be considered procedure related. All stroke events are considered serious. **Transient Ischemic Attack (TIA)** - New focal neurological deficit with rapid symptom resolution (usually 1-2h), always within 24 h. **Nerve Injury**- includes total or partial transection of a nerve from stretching, cutting (laceration), compression, shearing, or crushing injuries

- **Arteriovenous fistula** - A dilation of an artery with actual disruption of one or more layers of its walls, rather than with expansion of all wall layers. An arteriovenous fistula is an abnormal channel or passage between an artery and a vein.
- **Death** - Cessation of brain and heart activity documented by physician, laboratory or diagnostic test. Device related death is defined as death related to the investigational device. This may be a device malfunction, misuse, or any death in which the relation of the device cannot be ruled out.

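### The repeated-event rule in section 8.3.8 selects on severity alone, so a milder device-related occurrence can drop out of the relationship table

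*Combined protocol and SAP*

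**What the plan says.** Section 8.3.8 (Safety Evaluations and Analyses) sets out the tables: "The frequency of each event will be summarized by seriousness, severity and by relationship to the device". The next sentence deals with a subject who reports the same event several times: "the occurrence of the highest severity case of the event will be used for the purpose of analysis". The rule is not confined to the severity table. The plan has no separate rule for relationship or seriousness, and no tie-break for a related and an unrelated occurrence of equal severity.

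The three attributes are defined separately:

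- **Severity** (section 9.1.1) has three grades, based on interference with daily life and the treatment needed. The top grade covers an event that "requires substantial therapeutic measures including surgical intervention or hospitalization".
- **Relationship** (section 9.1.1) has two levels, the upper one being "Related: Clinical evidence supports a definite and certain causal relationship".
- **Seriousness** (section 9.1.3) depends on outcome. One of its criteria is that the event "results in an unanticipated or prolonged hospitalization".

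The second primary safety endpoint (section 8.2.1, Primary Endpoints) is "Overall device and procedure related anticipated adverse events compared to historical safety data from CV placement procedures". Section 8.3.5 says that the primary endpoints will be "summarized using number with the event or characteristic, the number evaluated, frequencies, percentages and two-sided exact 95% confidence intervals". It gives no rule for repeated events and does not refer to section 8.3.8.

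**The concern.** Keeping the worst case is a sound convention for a severity table, because it answers the question that table asks. Here the same selected record also feeds the relationship and seriousness tables, and severity decides neither of those.

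Take a subject with a severe infection unrelated to the device and a mild exit-site infection related to it, both recorded under the one term *infection*. The rule keeps the severe, unrelated record, and the relationship table then shows no related infection for that subject.

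At stake is the count of device-related events in a 30-subject single-arm study, where one subject visibly moves a percentage. One of the two primary safety endpoints is itself a count of related events, so it would be exposed if the analyst applied the same rule there.

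**Working it through.** **Inputs.** n = 30 (section 6.0); two-sided alpha 0.05 with exact binomial intervals (sections 8.3.1 and 8.3.5); the repeat rule (section 8.3.8); the severity and relationship scales (section 9.1.1); the seriousness criteria (section 9.1.3 and Appendix A). The documents give no rate of repeated events, so every event count below is an assumption.

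**Step 1: reproduce the plan's own precision figures.** For x events in n subjects, the Clopper-Pearson limits are:

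- lower = the alpha/2 quantile of Beta(x, n − x + 1)
- upper = the 1 − alpha/2 quantile of Beta(x + 1, n − x)

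For 27/30 this gives 73.5% to 97.9%, and for 15/30 it gives 31.3% to 68.7%. Both match section 8.2.2.

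**Step 2: direction of the error.** Take one subject and one event term. Under an any-occurrence count, the subject is related if at least one record is related. Under section 8.3.8, the subject is related only if the single retained record is related. That record is one of the subject's own, so the second condition implies the first but not the reverse. The rule can therefore remove a related subject and can never add one. The same logic applies to serious events.

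**Step 3: constructed example (assumed, not trial data).** Four subjects have a related event:

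| Subject | Event | Records |
|---|---|---|
| 1 | haematoma | mild, related; severe, unrelated |
| 2 | arrhythmia | moderate, related, serious; severe, unrelated, non-serious |
| 3 | pain | mild, related |
| 4 | bleeding | moderate, related |

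Any-occurrence count: 4 related subjects and 1 serious. Section 8.3.8 rule: 2 related and 0 serious, because subjects 1 and 2 each lose the milder record.

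**Step 4: size if the rule reached the second primary safety endpoint.** One subject is 1/30 = 3.3 percentage points.

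| Any-occurrence count (exact 95% CI) | After loss (exact 95% CI) |
|---|---|
| 1/30 = 3.3% (0.1 to 17.2) | 0/30 = 0.0% (0 to 11.6) |
| 3/30 = 10.0% (2.1 to 26.5) | 2/30 = 6.7% (0.8 to 22.1) |
| 4/30 = 13.3% (3.8 to 30.7) | 2/30 = 6.7% (0.8 to 22.1) |

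The last row is the example in step 3. It assumes that half of the subjects with a related event have such a pair, so it is an extreme illustration. The first two rows lose one subject each.

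**Step 5: can seriousness be lost?** Only in a narrow set of cases. The Severe grade already covers hospitalization, and an event that is fatal, life-threatening or permanently disabling would hardly be graded lower. Two gaps remain. Surgical intervention places an event in the Severe grade but is not a listed seriousness criterion. For arrhythmia, Appendix A says "Event that requires cardioversion or introduction of a pacemaker will be considered a Serious Adverse Event", whatever the severity grade. A severe non-serious arrhythmia could then displace a moderate one that was cardioverted. Strokes and tamponade are always serious under Appendix A, so nothing can be lost within those terms.

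**The case against.** **Section 8.3.8 could be read as taking the worst case within each category.** Its first sentence sorts events by seriousness, relationship and anticipation, and selection within those groups would lose nothing. But the sentence on repeats does not say this: it names one case per event, chosen on severity. The statements in sections 7.6 and 7.7 that all collected data will be included set no counting rule either.

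**The primary endpoint may be untouched.** A reader might infer that the second primary safety endpoint will be undercounted in the device's favour. The documents do not establish that. Section 8.3.5 does not cite section 8.3.8, which disclaims hypothesis testing and may be meant as a separate summary. Number with the event is naturally read as any related event, and a subject with another, retained related event would still count. This objection stands, so the effect on the endpoint is conditional.

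**Serious events would not be hidden.** A reader might infer a general loss of serious events. The overlap between Severe and the seriousness criteria makes that remote. Serious events are also reported individually under section 9.1.4, and the monitoring committee reviews adverse events clinically. This objection stands as well.

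**Such pairs should be uncommon.** One might argue that recurrent unrelated infection, thrombosis or arrhythmia is to be expected in dialysis or chemotherapy patients. Nothing in the documents supports that for a window of 7 to 14 days. Acute thrombosis in a vessel to be crossed and active endocarditis are exclusions, and Table 4 lists 2 complications in 136 patients. The plan also does not define what makes two reports the same event, so the infection example depends on a broad term being used.

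**Conclusion.** Wrong as written, with low impact. Followed literally, section 8.3.8 can drop a milder related occurrence from the relationship table and can never add one. This needs only the plain text of the rule and the separate scales in section 9.1.1.

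The size is conditional on three things: a subject has the same event at least twice during follow-up, the more severe occurrence is unrelated, and no other retained record keeps that subject in the related count at issue. If the rule is also applied to the second primary safety endpoint, each subject lost costs 3.3 points, and the intervals before and after a one-subject loss overlap heavily. The study is unpowered and states no success threshold for this endpoint, so no formal decision turns on the shift. The documents do not support a claim that the primary result is biased, or that serious events will generally be lost.

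**What to change.** Replace the repeat sentence in section 8.3.8 with:

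> A subject is counted once per event term in each table: at the highest severity in the severity table; as device- or procedure-related if any occurrence was related; as serious if any occurrence was serious.

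Add to section 8.3.5:

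> For the second primary safety endpoint, a subject counts if any occurrence of an anticipated event was device- or procedure-related.

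This also settles ties at equal severity, and it removes the need to choose a counting rule after the data are seen. The cost is a short text change, with no new data and no extra subjects.
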